# Study Protocol and Statistical Analysis Plan

The present study recruited children suffering from SAR during the pollen season. They had a poor control of SAR despite antihistaminic treatment (cetirizine 2.5 mg bid in preschoolers or 5 mg bid in schoolers). SAR diagnosis was performed according to validated criteria. Allergy was defined if nasal symptom history was consistent with documented sensitization.

Inclusion criteria were: age range 4-12 years, SAR diagnosis, Total Symptoms Score (TSS)  $\geq$  6, and written informed consent of both parents or legal guardians. Exclusion criteria were: perennial AR, rhinitis due to other causes, concomitant acute or chronic rhinosinusitis, nasal polyps, asthma comorbidity, current use of topical or systemic corticosteroids, antihistamines, antileukotrienes, inadequate washout of them, nasal anatomic defect, respiratory infections in the last two weeks, participation in other clinical studies in the previous month, documented hypersensitivity to the study product or its excipients, and trip planned outside of the study area.

The study was conducted in a third-level pediatrics department located in Southern Italy. The study procedure was approved by the local Ethics Committee (Prt n 408, 20/06/2019).

Children were randomly (ratio 1:1) subdivided into two groups: the active group treated with MFNS (Mometasone group) and the control group treated with isotonic saline. For both groups, the schedule was for one spray into each nostril (MFNS 50 mcg/spray) twice a day for 21 days.

The participants were evaluated at baseline (T0), after 7 (T1) and 21 (T2) days, and 30 days (T3) after treatment discontinuation.

During the study, systemic or intranasal antihistamines, other corticosteroids, leukotriene antagonists, and sodium cromoglicate were prohibited.

The primary endpoint of this study was the change in eosinophilic infiltrate, assessed by nasal cytology, after the treatment. The secondary objectives were the nasal mast cell and neutrophil count, symptom severity, and QoL changes during the study.

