The statistical analysis included different tests. Shapiro-Wilk test was performed to investigate continuous variables distribution. Differences between the active and control group were tested with Mann-Whitney U test for independent samples. Longitudinal changes for continuous variables were investigated by Wilcoxon signed-rank test for paired samples. Delta changes in questionnaires scores were calculated for each group as T1-T0 scores for the control group, T2-T0 scores, and T3-T0 scores for the mometasone group. Differences in delta changes between groups were investigated by Mann-Whitney U test. Chi-square test and Fisher exact test were performed for differences in categorical variables. A  $p \leq 0.05$  was considered statistically significant. Data were expressed as median (interquartile range) or as a percentage as appropriate. All analyses were performed with SAS® on Demand for Academics (Cary, NC: SAS Institute Inc.)

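### As written, the questionnaire change scores are taken at different visits in the two arms, so comparing them between groups is not a same-visit contrast

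*Combined protocol and SAP*

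**What the plan says.** The combined document has one heading, Study Protocol and Statistical Analysis Plan. Its design text describes a parallel-group trial with a common timetable:

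- Allocation: "Children were randomly (ratio 1:1) subdivided into two groups".
- Treatment period: "For both groups, the schedule was for one spray into each nostril (MFNS 50 mcg/spray) twice a day for 21 days".
- Visits: "The participants were evaluated at baseline (T0), after 7 (T1) and 21 (T2) days, and 30 days (T3) after treatment discontinuation". No visit is restricted to one arm.

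The closing paragraph on statistical analysis defines the change scores for questionnaires as "calculated for each group as T1-T0 scores for the control group, T2-T0 scores, and T3-T0 scores for the mometasone group". The next sentence gives the test: "Differences in delta changes between groups were investigated by Mann-Whitney U test".

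Two other sentences in that paragraph bear on the point. One is a general between-group test that names no visit: "Differences between the active and control group were tested with Mann-Whitney U test for independent samples". The other is a paired test, and so a within-arm one: "Longitudinal changes for continuous variables were investigated by Wilcoxon signed-rank test for paired samples".

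**The concern.** The definition ties T1-T0 to the control group and T3-T0 to the mometasone group. T2-T0 has no label of its own and reads most naturally with mometasone. If the changes are formed that way and compared between groups, control children early in treatment are set against mometasone children at the end of treatment or a month after it. Nothing in the design calls for arm-specific visits.

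Randomisation makes the arms comparable at a given visit. It does not make one arm at day 7 comparable with the other at day 21 or day 51. A shift in scores over time cannot be assumed absent here: "The present study recruited children suffering from SAR during the pollen season", and T3 comes 30 days after treatment ends. Higher scores mean worse symptoms or quality of life. Scores that fall over time would therefore flatter mometasone, and scores that rise would hide a benefit. Symptom severity and quality of life are named secondary objectives, so these contrasts bear on stated aims.

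**Working it through.** The plan states no sample size, SD, power or time trend, so it has no figure to reproduce. The check is of wording and timing, followed by a labelled illustration.

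**1. Visit days.** From the visit schedule, taking the 21-day course as completed: T1 = 7, T2 = 21, T3 = 21 + 30 = 51.

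**2. Possible readings of the definition.**

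| Reading | Control | Mometasone | Visits shared | Gaps between mismatched visits (days) |
|---|---|---|---|---|
| Literal: T2-T0 goes with mometasone | T1 | T2, T3 | 0 of 3 | 21 − 7 = 14; 51 − 7 = 44 |
| T2-T0 goes with control | T1, T2 | T3 | 0 of 3 | 51 − 7 = 44; 51 − 21 = 30 |
| T2-T0 applies to both | T1, T2 | T2, T3 | 1 of 3 (T2) | 14, 44 and 30 |
| All three changes in both arms, labels misplaced | T1, T2, T3 | T1, T2, T3 | 3 of 3 | none |

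Only the last reading gives a same-visit contrast throughout.

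**3. What a mismatched contrast estimates.** Let M(t) and C(t) be the mean change from baseline at visit t in the mometasone and control arms. Then

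M(T2) − C(T1) = [M(T2) − C(T2)] + [C(T2) − C(T1)].

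The first bracket is the randomised treatment effect at T2. The second is the drift in the control arm from day 7 to day 21. Replacing T2 by T3 gives the corresponding result for day 51. The bias is the drift, which the document gives no means of estimating.

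**4. Illustration on assumed values.** Take normally distributed changes with SD 1, no treatment effect, the same drift in both arms, and a two-sided Mann-Whitney U test (normal approximation) at p ≤ 0.05, with 20,000 simulated trials per cell. The arm sizes, SD and drifts are assumptions, not trial values. Rejection rates for the mismatched contrast:

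| Drift between visits | 20 per arm | 30 per arm | 50 per arm |
|---|---|---|---|
| 0 | 5.2% | 4.8% | 4.7% |
| 0.25 SD | 11.5% | 14.9% | 22.5% |
| 0.5 SD | 32.5% | 45.3% | 67.6% |

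In a separate simulation of 4,000 trials per cell, with drifts from 0 to 1 SD, the same-visit comparison rejected in 4.1% to 5.7%. Independently of sample size, the probability that a random mometasone change lies below a random control change is Φ(drift/√2) when scores fall. That is 0.500, 0.570 and 0.638 for drifts of 0, 0.25 and 0.5 SD.

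**5. Two-week symptom score.** This applies only if that score counts as a questionnaire score, looks back 14 days, and treatment starts on day 0. Control at T1 would cover days −7 to 7 (7 before treatment, 7 on it). Mometasone at T2 would cover days 7 to 21 (14 on treatment), and at T3 days 37 to 51 (14 off treatment). On the literal reading the arms would then differ in treatment phase as well as in date.

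**The case against.** The strongest reply is that this is a drafting slip. The sentence begins by referring to each group, the three changes it lists are the three post-baseline visits in order, and both arms have the same timetable. All of that fits a plan to calculate every change in both arms. Nor does the test sentence name visit pairs, so setting day 7 against day 21 and day 51 is an inference from the labels. The general Mann-Whitney comparison may supply same-visit results for the same scores. The rejection rates in the illustration are ordinary power for a shift in location, and with no drift the error rate stays near 5%.

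Much of this stands. The slip is plausible, mismatched testing is not shown, and the illustration says nothing about this trial's actual error. It does not rescue the definition, however. The arm labels are explicit for T1-T0 and T3-T0, and no other sentence corrects them. The general test names no visit, so it cannot be relied on to supply the matched contrast. The paired test works within arms. A reader cannot tell from the document which comparison was made.

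**Conclusion.** The point holds. As written, the definition of change scores is wrong for a randomised comparison: on the literal reading no post-baseline visit is shared, and the arms are compared 14 and about 44 days apart. Only one of the four readings gives matched visits throughout. Confidence is high about the wording. Whether mismatched changes were intended or used is not shown.

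The size and direction of any bias are unknown, because they depend on a between-visit drift that the document does not report. The day-51 figure assumes a completed 21-day course. The scope is limited to secondary outcomes: the PRQLQ is the only instrument called a questionnaire, and the symptom score and VAS are affected only if they fall under that term. The sentence does not govern the eosinophil primary endpoint, and it does not tie the general between-group test to particular visits. This should be fixed, but it does not by itself undermine the main analysis.

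**What to change.** 1. The text is in the past tense, so first state which changes were actually compared, for which scores, in which arms and at which visits.
2. Replace the definition with: *For each score, T1-T0, T2-T0 and T3-T0 are calculated in both groups, and the groups are compared only at the same visit.*
3. Name the scores covered: the PRQLQ and, if intended, the symptom score and VAS.
4. If any mismatched contrast was used, drop it and re-run the comparison at the same visit. Label as post hoc any main visit chosen after the data were seen.

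The cost is one or two sentences of plan wording, plus a re-run only if mismatched contrasts were used. The visits needed are already scheduled for all participants. The document does not show how complete the control data are at T2 and T3, so that should be reported with any re-run.

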Nasal cytology is a well-defined methodology. The procedure included sampling, processing, and microscope reading. Sampling required collecting cells from the surface of the middle portion of the inferior turbinate by a sterile disposable curette. The procedure was performed under anterior rhinoscopy, with an appropriate light source, and it was painless. The sample obtained was immediately smeared on a glass slide, air-dried, and stained with May-Grünwald-Giemsa (MGG) for 30 minutes. Next, the stained sample was read at optical microscopy, with a 1000x objective with oil immersion. The count of eosinophils, neutrophils, and mast cells was expressed as a mean of 10 microscopic fields.

The validated Pediatric Rhinoconjunctivitis Quality of Life Questionnaire (PRQLQ) consists of 23 questions in 5 domains (nasal symptoms, ocular symptoms, practical issues, limitation of activities, other symptoms) that are answered on a 7-point scale (0-6), where 0 represents the absence of problems and 6 the greatest symptom distress. Children will complete the questionnaire together with a parent at baseline and during the study. A Total Score was calculated as the mean of the 5 domains.

Total symptom score was the sum of 3 domains: i) nasal symptoms (TNSS) included itching, sneezing, rhinorrhea, nasal congestion; ii) ocular symptoms (TOSS): itching, hyperemia of the conjunctiva, tearing; and iii) throat symptoms (TTSS): itching, coughing. With the help of their parents, patients scored symptoms severity on a 4-point scale: 0 = absent or irrelevant, 1 = mild, 2 = moderate, 3 = severe. Total symptom score was assessed at 12 hours (TTS 12h) and two weeks (TTS 2W) before the visits. TSS represents the doctor's point of view of symptom severity.

A visual analogic scale (VAS) measured the parental perception of symptom severity (0=no symptom; 10=very severe symptoms).

Safety was assessed on the incidence of adverse events for each treatment and physical examination.

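### A single unadjusted 0.05 rule covers all secondary outcomes and visits, with no key visit, multiplicity control or exploratory label

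*Combined protocol and SAP*

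**What the plan says.** All passages are in the combined protocol and SAP, under the heading Study Protocol and Statistical Analysis Plan.

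- **Threshold.** The statistical analysis paragraph gives one rule: p at or below 0.05 "was considered statistically significant". It follows a list of between-group, within-group, delta-change and categorical tests, and makes no distinction among them.
- **Primary endpoint.** There is one: "The primary endpoint of this study was the change in eosinophilic infiltrate", assessed after treatment. No visit is named.
- **Secondary objectives.** "The secondary objectives were the nasal mast cell and neutrophil count, symptom severity, and QoL changes during the study".
- **Visits.** "The participants were evaluated at baseline (T0), after 7 (T1) and 21 (T2) days, and 30 days (T3) after treatment discontinuation".
- **Symptom measures.** "Total symptom score was assessed at 12 hours (TTS 12h) and two weeks (TTS 2W) before the visits". A parental VAS is a third measure of symptom severity.
- **Quality of life.** A PRQLQ total is formed as the mean of five domains.
- **Between-group tests.** Differences between the arms "were tested with Mann-Whitney U test for independent samples". A second set of Mann-Whitney tests compares delta changes in questionnaire scores. The sentence defining those deltas gives T1 minus T0 to the control group, and T2 minus T0 and T3 minus T0 to the mometasone group.

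Nowhere do the documents give a multiplicity adjustment, an order among the secondaries, a key visit, an exploratory label or a list of tests.

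**The concern.** The plan attaches the same significance label to every test. Symptom severity alone has three summary measures and three post-baseline visits, so there may be nine between-arm chances to report it as significant. Nothing written in advance says which of these carries the claim. A reader cannot tell a pre-chosen secondary result from one picked out because its p-value happened to be small.

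This matters because symptoms and quality of life, the outcomes that children and parents notice, are all secondary here. Naming a single primary endpoint protects the eosinophil claim. It gives no protection to these.

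**Working it through.** The plan states no test count, familywise error rate or sample size, so it has no figure to reproduce. The check asks how often at least one secondary test reaches p ≤ 0.05 when the arms do not differ on anything.

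**Inputs from the documents**
- Per-test threshold: 0.05.
- Secondary summary measures: neutrophils, mast cells, TTS 12h, TTS 2W, VAS and PRQLQ total, making 6.
- Post-baseline visits: T1, T2 and T3, making 3.

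**Assumptions**
- Each measure is compared between arms once at each visit: 6 × 3 = 18 tests. The documents do not say this.
- Tests are two-sided. Sidedness is not stated.
- Each comparison uses the same visit in both arms, so each has a 5% error rate.
- Correlations between measures and between visits are assumed, because the documents give none. Test statistics are treated as multivariate normal, with the correlation between any two equal to the product of the measure and visit correlations unless noted.

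**Independent tests (upper reference)**
- Any false finding, 18 tests: 1 − 0.95^18 = 60.3%.
- Any false finding, 9 tests: 1 − 0.95^9 = 37.0%.
- False benefit only (2.5% tail), 18 tests: 1 − 0.975^18 = 36.6%.

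**Positively correlated tests (simulation, 300,000 or more draws per row)**

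| Tests | Correlation between measures / visits | Any false finding | False benefit only |
|---|---|---|---|
| 6 × 3 | common 0.2 among all 18 | 55.5% | 29.6% |
| 6 × 3 | 0.3 / 0.3 | 54.6% | 29.7% |
| 6 × 3 | 0.5 / 0.5 | 45.3% | 23.3% |
| 6 × 3 | 0.7 / 0.5 | 37.0% | 18.7% |
| 6 × 3 | 0.7 / 0.7 | 32.7% | 16.4% |
| 3 × 3 | 0.5 / 0.5 | 29.3% | 14.9% |
| 3 × 3 | 0.7 / 0.7 | 22.6% | 11.3% |

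For 18 tests the range is about 33–56% for any false finding and about 16–30% for a false benefit. Weaker correlation moves the figures towards the independence values. The lower end is not a floor: a common correlation of 0.7 among all 18 statistics gives about 28%.

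**Would naming one visit be enough?** Six unadjusted tests at a single visit give 1 − 0.95^6 = 26.5% if independent, and about 21% at a common correlation of 0.5. Some adjustment within the six is still needed.

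**After adjustment.** The first Holm step for six tests is 0.05/6 = 0.0083. The chance that any of six independent tests passes it is 1 − (1 − 0.05/6)^6 = 4.9%. Holm keeps the rate at or below 5% under any correlation.

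**The case against.** The strongest reply is that the plan names one primary endpoint and calls the rest secondary. The significance rule is a per-test label. The plan states no familywise rate and no rule that one positive secondary proves efficacy, and strict familywise control of secondaries in a single-centre study is partly a matter of preference. Much of this stands. The error rate of the primary claim is untouched, and labelling the secondaries exploratory would resolve the point. But the plan does not so label them; it gives them the same significance label as the primary.

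Three stronger readings are tempting and are not supported.

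- **That at least 18 tests will be run, with a 60% false-positive rate.** Eighteen is an inference. No passage lists the tests or says that every measure is compared at every visit, and the delta sentence assigns different visits to the two arms, so the number of delta comparisons is unclear. The 60% also needs independence. TTS 12h and TTS 2W score the same symptoms over nested look-backs, and VAS rates overall symptom severity, so they are very unlikely to be independent.
- **That sub-domains raise the count to 51 and the rate to 93%.** That count takes 17 measures (the six above, three symptom domains at two look-backs, and five PRQLQ domains) at three visits. The documents define the domains as components of totals ("Total symptom score was the sum of 3 domains") and do not say that each is tested. A total cannot be independent of the domains that make it up, so the 93% cannot arise.
- **That the trial has this chance of falsely showing benefit.** The two-sided figures count harm as well as benefit. False benefit is about half as likely.

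In the other direction, the within-arm Wilcoxon tests and the second set of Mann-Whitney tests fall under the same threshold and are not counted. If deltas are compared across different visits as written, even the 5% per-test rate is not assured, because symptoms can change with time.

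**Conclusion.** The point holds as an absence of error control for the secondary claims. Its size depends on a test list that the plan does not give. In every scenario tabulated the chance of a false secondary finding is more than four times 5%, and none of the qualifications brings it near the nominal level.

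The conclusion rests on two-sided tests, same-visit comparisons and assumed correlations. It is a point to correct, and does not invalidate the trial's primary analysis.

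**What to change.** 1. Keep the change in eosinophils as the single primary test at two-sided 0.05, and state the visit at which it is assessed.
2. Correct the delta sentence so that both arms are compared at the same visit, using T2 minus T0 in each. No T2 delta comparison can be run until this is done.
3. Apply Holm to the six T2 between-arm secondaries: neutrophils, mast cells, TTS 12h, TTS 2W, VAS and PRQLQ total. The smallest p-value must be at or below 0.0083.
4. Report T1, T3, sub-domain and within-arm results as exploratory estimates with intervals, without the significance label.

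Labelling all secondaries exploratory is an acceptable alternative to step 3. Testing the secondaries only if the eosinophil result is significant is optional: it would put primary and secondary claims under one 5% rate, but would block every symptom and quality-of-life claim if the cytology endpoint misses.

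**Cost.** No new data, visits or participants are needed. An individual secondary needs a smaller p-value before it can be claimed, and T1 and T3 results cannot be claimed as confirmed. The text is mostly in the past tense, so the analyses may already be done. In that case Holm can still be applied to the same-visit T2 p-values, but the choice of visit and the adjustment must be disclosed as post hoc.
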